5 TREATMENT OF SUBJECTS

Subjects will receive a single dose of IMP in one (study) eye. The IMP will be randomized as either AG-920 or Placebo. The study eye will be randomized as either right eye (OD) or left eye (OS). The single dose will be administered by the clinic staff as two drops in study eye 30 seconds apart.

5.1 *Concomitant medications*

5.1.1 **Prohibited medications**

The list of prohibited medications provided below may not be comprehensive. Investigators are encouraged to consult with the Medical Monitor for a decision about proceeding if they have any questions or concerns about any medication.

The following medications are prohibited.

- systemic opioids or opiate analgesics within 30 days of randomization and during the study treatment day
- topical NSAIDs within 30 days of randomization and during the study treatment day
- Over-the-counter (OTC) artificial tear lubricant products within one hour preceding or following study medication, other than the tolerability test

As noted in the exclusion criteria (Section 4.2), individuals must refrain from contact lens wear on the Dosing and Anesthesia Testing Day.

5.1.2 **Allowed medications**

Other than the agents and/or times noted above, systemic therapy with agents is allowed.

Use of all medications should be documented on the appropriate CRF. Investigators are encouraged to contact the Sponsor for any questions regarding allowed medications. Judgment of continued study participation by the subject, and inclusion of this subject's subsequent visits in the safety and efficacy analysis will be made by the Sponsor.

All medications which the subject has taken within 30 days prior to screening and during the study will be recorded in the CRF. The name of the drug, dose, route of administration, duration of treatment and indication will be recorded for each medication. For combination products (e.g., Contac®), the brand name is required. For non-combination products, the generic name is desired. The use of routine ophthalmic diagnostic pharmaceutical agents (e.g., fluorescein and local anesthetic) will be allowed, and individual documentation not required.

5.2 *Female Subjects*

Female subjects of childbearing potential must not be pregnant or breastfeeding at Randomization. These subjects must have a negative urine pregnancy test at Screening in order to be eligible for the study.

Female subjects who are not of childbearing potential must meet at least one of the following criteria:

- At least 1 year since the last menstrual period
- Surgically sterile (tubal ligation, bilateral oophorectomy, salpingectomy, or hysterectomy)
- Congenitally sterile
- Diagnosed as infertile and not undergoing treatment to reverse infertility

6 STUDY PROCEDURES

6.1 General Procedures:

The study will consist of 1 or 2 clinic visits and 1 Follow-up Phone Call. All ocular assessments will be performed on both eyes. Subjects will be screened for entry (Visit 1) and randomized/treated at (Visit 2). Visit 1 and 2 may be on the same day. At randomization, subjects will receive a single dose of IMP (2 drops 30 seconds apart) in the study eye. Subjects will then have a safety Follow-up Phone Call 1-4 days (Days 2-5) following Visit 2.

6.2 Re-screening Procedures:

A subject who is first designated as a screen failure prior to being randomized will be allowed to rescreen one additional time 7-30 days later.

6.3 Visit 1 (Screening) – Day -2 to 0/1

Visit 1 may be combined with Visit 2 in order to accommodate clinic logistics. If both visits are combined, Visit 1 will last anywhere from 1-3 hours. If topical anesthetic drops are used to assess IOP, subject must wait at least 1 hour before IMP treatment. Topical anesthetic drops may cause a mild stinging or burning sensation upon instillation.

The following procedures will be performed in the following suggested order at Visit 1. All ocular tests at this and all visits will be performed in both eyes (with the exception of conjunctival pinching):

- Obtain written informed consent to participate before any study-required screening assessments have been conducted
- Collect demographics (sex, year of birth, race, ethnicity)
- Collect systemic medical history and ocular medical history
- Review of prior and concomitant medications (including ocular medications)
- Study technician to instill a drop of an Over-The-Counter artificial tear. At the opinion of the Investigator/Study Technician, only individuals who tolerate this drop, will be enrolled.
- Perform urine pregnancy test (UPT) on women of childbearing potential (see Appendix 1).
- Measure Best Corrected Visual Acuity (BCVA) (see Appendix 1)
- Perform slit lamp biomicroscopy and external eye exam (see Appendix 1)
- Measure IOP (see Appendix 1)
- Verify subject eligibility based on Inclusion/Exclusion requirements
- Schedule subject to return for Visit 2 if Visit 1 and 2 are not performed on the same day.

6.4 Visit 2 (Randomization/Treatment) – Day 1

Visit 2 must occur within 3 days of Visit 1 (Screening) if it is not performed on the same day as Visit 1. As noted in Section 6.3, Visit 1 and Visit 2 may be performed on the same day for clinic logistics. If a topical anesthetic is used to measure IOP at Screening (Visit 1), there must be at least a 1-hour interval post-anesthetic drops prior to treatment with IMP. At Visit 2, subjects are expected to be in the clinic for approximately 60 minutes post dose.

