1.2 Potential Risks and benefits to human subjects

Minimal risks are expected with AG-920. The most common risks associated with [REDACTED]® ([REDACTED] [REDACTED]) are headache and pain. The incidence of these adverse events occur in 4% and 13% of patients respectively. These adverse events of [REDACTED] are following [REDACTED] injection, where AG-920 is applied topically to the eye ([REDACTED] [Package Insert](#)).

Expected risks for subjects may include a temporary mild to moderate stinging or burning sensation upon instillation of the investigational medical product (IMP). Temporary mild hyperemia may also occur following instillation. For any additional information on AG-920 use, please refer to the [Investigator's Brochure](#).

As this study is to be conducted in healthy subjects, there is no anticipated benefit other than the possibility that a subject's participation in the present study may help others in the future to have more options for local anesthesia before ophthalmic procedures.

Adverse events (AEs) not reported in previous clinical trials but present among subjects in this clinical trial will be communicated to Investigators and to ethics committees or Institutional Review Board (IRBs) in accordance with local regulations.

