4 SUBJECT INCLUSION AND EXCLUSION CRITERIA

Subjects must meet all of the following inclusion criteria to be eligible for participation in this study. On criteria that involves the eyes, both eyes must qualify.

4.1 *Subject inclusion criteria*

1. Provide written informed consent prior to any study-related procedures being performed.
2. Is male or a non-pregnant, non-lactating female aged 18 years or older. Female subjects of childbearing potential must have a negative urine pregnancy test at Screening (Visit 1) in order to be eligible for randomization.

3. Are willing and able to follow instructions and can be present for the required study visits and Follow-up Phone Call for the duration of the study.
4. Have an Early Treatment of Diabetic Retinopathy Study (ETDRS) best corrected visual acuity (BCVA) of 20/200 or better in each eye as assessed by Early Treatment of Diabetic Retinopathy Study (ETDRS) at the screening visit. Note: previous refractive procedures allowed.
5. Have an Intraocular Pressure (IOP) between 7 and 30 mmHg.
6. Certified as healthy by clinical assessment (detailed medical history) including ocular examination.
7. Verbal communication skills adequate to participate.
8. Able to tolerate bilateral instillation of Over-The-Counter artificial tear product based on investigator judgement.

4.2 *Subject exclusion criteria*

Subjects who meet any of the following exclusion criteria are ineligible for this study:

1. Have participated in an investigational study (drug or device) within the past 30 days.
2. Have a contraindication to local anesthetics, [REDACTED]®, or any component of the IMP.
3. Have known decreased corneal or conjunctival sensitivity (e.g., sequelae of herpetic eye disease, corneal graft) or a diagnosed corneal pathology which might lead to decreased sensitivity.
4. Have had ocular surgery (intraocular, refractive, extraocular muscles, eyelid) or general surgery in either eye within the past 90 days (Note: [REDACTED] restorative work allowed)
5. Have had an intravitreal injection in either eye within 14 days of randomization.
6. Have ocular surface disease requiring punctual plugs.
7. Evidence of any current ocular inflammation.
8. Subject who must wear contact lenses on Study Day 1 (Visit 2).
9. Are currently using, or used within the past 30 days, a systemic opioid or opiate analgesic or topical Non-steroidal Anti-Inflammatory Drug (NSAID).

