Appendix 1: Procedures

Procedures: Best Corrected Visual Acuity

Introduction: Best corrected visual acuity (Distance) will be measured at Visit 1 and at the end of Visit 2. Visual acuity will be measured using Bailey Lovie charts, ETDRS charts, or their equivalents. Accepted charts are those designed according to the following principles described by [Bailey and Lovie \(1976\)](#), [Ferris et al \(1993\)](#) and the National Academy of Science-National Research Council (NAS-NRC) Committee on Vision 1980 (1980): 1) letters of equal legibility; 2) combine the letters so that each line is of approximately equal difficulty (as described by Ferris et al, 1993); 3) present five letters at each acuity level; 4) space rows by the height of the smaller letter 5) space letters by the width of same-sized letters and 6) use a logarithmic progression of letter size from logMAR (Minimum Angle of Resolution to base 10) -0.3 (20/10) to 1.0 (20/200).

Rationale: Best corrected acuity taken at follow-up visits as a measure of ocular function. Best corrected visual acuity will be measured at screening and frequently throughout the study.

Procedure: Distance visual acuity must be assessed using an Early Treatment of Diabetic Retinopathy Study (ETDRS) or equivalent chart. Visual acuity testing should precede intraocular pressure measurement, the administration of topical anesthetic agents, or any examination requiring contact with the anterior segment.

Distance visual acuity will be measured with best correction.

The visual acuity chart may be either retro-illuminated (“back-lit”), or reflectance illuminated. If the latter, then the illumination must be checked at regular intervals to be consistent with ETDRS guidelines. Standard charts for a distance from subject to chart of 10 feet to 20 feet must be used. Ideally, the subject should be seated. The right eye should be tested first. Sites are directed to refer to the instructions on the commercial ETDRS charts. If there is any question, contact the Sponsor’s monitor.

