5.1. Presentation of Summaries and Analyses

In general, continuous data will be summarized by descriptive statistics, i.e., n, mean, standard deviation (SD), median, minimum and maximum values, and categorical data will be summarized using counts (N: number of subjects per treatment group, n: number of subjects with non-missing values) and percentages. Percentages will be suppressed when the count is zero, however the category will still be displayed. The denominator for all percentages will be the number of subjects per treatment in the analysis set of interest (%: n/N*100), unless otherwise indicated.

In general, and unless specified otherwise, all data summaries will be sorted by the parameter under consideration and then by visit. Listings will be sorted as per subject ID, the parameter under consideration and then by visit.

Unless otherwise stated, baseline will be defined as the last value of the assessment recorded prior to first study drug administration.

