9.2. Other Safety Parameters

Best corrected visual acuity and slit lamp biomicroscopy will be measured at Visit 1 (screening) and at the end of Visit 2. BCVA will be measured in logMAR units and results will be summarized using descriptive statistics for the Visit 1 and Visit 2 values and for the changes from Visit 1 to Visit 2. Results will be presented separately for the study eye and non-study eye.

The biomicroscopy grading scales are given in Appendix 1 of the protocol; the following assessments will be done on four anterior locations of each eye:

- Lid (erythema and edema)
- Conjunctiva (hyperemia and edema)
- Cornea (edema)
- Anterior chamber (cells and flare)

The data for each assessment will be summarized using counts and percentages of eyes within each category and will be summarized for the Visit 1 and Visit 2 values and for the changes from Visit 1 to Visit 2. Results will be presented separately for the study eye and non-study eye.

10. Software Used for Analysis

SAS Software Version 9.4 or higher (SAS Institute Inc., Cary, NC), will be used for the statistical analysis and statistical reporting.

11. Changes from the Protocol

The variables and methods described in this plan will supersede those described in the protocol.

12. Requirements and Specifications (Mock-shells) for Programming and Presentation of Tables, Listings and Figures (TLFs)

This document is intended to be used only as a guide in the development of TLFs and may be adjusted to meet study and Sponsor specific needs.

The specifications for the TLFs must follow the description in the associated Statistical Analysis Plan (SAP).

The following details the requirements and specifications for the programming and presentation of the TLFs, as set out in the TLF shells.

- A separate RTF document will be created for each TLF.
- All TLFs will be produced in a landscape format, as far as is feasible.
- The margin, page size specifications are stipulated below and will be used for the presentation of all TLFs:

| Item: | Specification: |
|--------------------|----------------|
| Page Layout | Landscape |
| Paper Size | 8.5 x 11 inch |

- The standard font size and font type are "9 point", "Courier New" for all TLFs.
- Every page of each output will have a header indicating the Sponsor name and protocol number (to be presented as set out in the example below).

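### The suggested Visit 1 order puts an eye drop ahead of the only pre-dose visual acuity and slit-lamp examinations, so the safety baseline may carry a transient effect of that drop (minor, easily removed)

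*Protocol*

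**What the plan says.** **Order at Visit 1.** Protocol Section 6.3 introduces its list with "The following procedures will be performed in the following suggested order at Visit 1". Within the list, "Study technician to instill a drop of an Over-The-Counter artificial tear" comes first, then the urine pregnancy test where applicable, then BCVA, slit lamp and IOP. Inclusion criterion 8 shows that both eyes are treated: "Able to tolerate bilateral instillation of Over-The-Counter artificial tear product based on investigator judgement". No interval between the tear and either examination is stated.

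**What acuity testing is protected from.** Protocol Appendix 1 says: "Visual acuity testing should precede intraocular pressure measurement, the administration of topical anesthetic agents, or any examination requiring contact with the anterior segment". The tear is not on that list.

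**What counts as baseline.** SAP 5.1 says "baseline will be defined as the last value of the assessment recorded prior to first study drug administration". SAP 9.2 says "Best corrected visual acuity and slit lamp biomicroscopy will be measured at Visit 1 (screening) and at the end of Visit 2". The pre-dose steps in Protocol Section 6.4.1 cover eligibility and changes in health or medication, with no repeat of either examination.

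**What is expected after dosing.** Protocol Section 1.2 lists stinging or burning, and adds: "Temporary mild hyperemia may also occur following instillation".

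**Tears near dosing.** Protocol Section 5.1.1 prohibits "artificial tear lubricant products within one hour preceding or following study medication, other than the tolerability test". Tear use around dosing is therefore controlled, but tear use around the baseline examination is not.

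**The concern.** Safety and tolerability is a stated secondary objective, and acuity and biomicroscopy are two of its named measures. Each has one pre-dose value. Under the suggested order that value is taken after a drop whose purpose is to find eyes that do not tolerate instillation. For men, and for women not of childbearing potential, no listed step separates the drop from BCVA.

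If the drop left an eye mildly red, the baseline grade would be 1, and the same grade after dosing would be tabulated as no change. If it altered acuity, the change to Visit 2 would be offset by that amount, in whichever direction the drop acted. The Visit 2 examination comes 15 to 60 minutes after the last pinch, so the two examinations would also differ in their timing after a drop. Appendix 1 asks for acuity to be tested under consistent conditions throughout.

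**Working it through.** **1. The plan's stated design figure.** Protocol 9.2 and SAP 3.2 give 88% power for 40% vs 15%, 60 per arm, two-sided alpha 0.05. With the pooled-variance chi-square, the mean proportion is 0.275.
- Null SE = sqrt(2 × 0.275 × 0.725 / 60) = 0.0815.
- Alternative SE = sqrt((0.15 × 0.85 + 0.40 × 0.60) / 60) = 0.0783.
- Power = Φ((0.25 − 1.96 × 0.0815) / 0.0783) = 87.6%.

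The 88% reproduces. Nothing below depends on it, and the fix does not change it.

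**2. Is the baseline post-tear?** Section 6.3 puts the tear before both examinations; SAP 9.2 has one pre-dose measurement of each; Section 6.4.1 adds none; SAP 5.1 takes the last pre-dose value. So if the suggested order is followed, the baseline is a post-tear value. Because the order is only suggested, this may differ between subjects.

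**3. Hyperemia (illustration).** Let q be the true rate of new mild hyperemia after dosing, and t the share of eyes graded 1 at baseline because of the tear, independent of any effect of the study product. The observed 0-to-1 rate is q(1 − t). The values of q and t are assumed.

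| t | q = 30% reads as | q = 10% reads as | Difference |
|---|---|---|---|
| 0% | 30% | 10% | 20 points |
| 5% | 28.5% | 9.5% | 19 points |
| 10% | 27% | 9% | 18 points |
| 20% | 24% | 8% | 16 points |

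The ratio between arms stays at 3.0. The absolute rates and their difference shrink by the factor 1 − t.

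**4. Acuity, mean change.** Each letter is 0.02 logMAR (Appendix 1). If the tear worsens baseline by b letters, mean change is shifted towards improvement by 0.02b; at an assumed b = 5 this is 0.10 logMAR. If the tear improves baseline acuity, b is negative and the shift is towards worsening. With the same average b in both arms, the difference in mean change is (μA − b) − (μP − b) = μA − μP, so it is unaffected.

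**5. Acuity, three-line worsening.** Three lines are 15 letters, or 0.30 logMAR. With baseline shifted by b, an eye is flagged only if its true loss is at least 15 + b letters. For true loss with mean μ and SD 5 letters (assumed), the flagged share is 1 − Φ((15 + b − μ)/5).

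| μ | b = 0 | b = 1 | b = 2 | b = 5 |
|---|---|---|---|---|
| 0 | 0.13% | 0.07% | 0.03% | 0.0% |
| 5 | 2.3% | 1.4% | 0.8% | 0.1% |
| 15 | 50% | 42% | 34% | 16% |

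The effect is large only if the average true loss is itself about three lines. At b = −5 and μ = 15 the share would be 1 − Φ(−1) = 84%, which is an overstatement.

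**6. Does adverse event reporting cover the gap?** Not fully. The note closing Protocol Section 8.3.1.3 keeps a condition that was present before masked medication, and has not worsened, off the adverse event record. Mild redness at a post-tear baseline that is again mild after dosing could therefore be absent from both the change table and the adverse event record.

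**The case against.** The strongest reply is that no harm is shown. The documents nowhere say that an artificial tear reddens the eye or alters acuity, or that any effect lasts until testing. They call the product a lubricant, so acuity could even improve. Subjects who do not tolerate the drop are not enrolled, and grade 1 in Appendix 1 calls for visible color change in both the bulbar and the palpebral conjunctiva. This stands, and it is why every effect size above is an assumption.

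The planned outputs also give protection. SAP 9.2 summarizes Visit 1 and Visit 2 values as well as changes, so post-dose hyperemia is reported as an absolute rate. Study and non-study eyes are shown separately, and the non-study eye receives the tear without the study product, so a tear artefact should be visible there. This largely stands, although the SAP plans no comparison between eyes, and an absolute Visit 2 rate does not show which redness is new.

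The three-line argument is thin. Protocol 9.4.7 plans that proportion, but SAP 9.2 lists only descriptive logMAR values and changes, and the SAP states that it supersedes the protocol's methods.

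Testing tolerability first also spares a failing subject further examination. That is a fair reason for the present order, and it is the price of the fix. A slit lamp done first might involve a diagnostic drop such as fluorescein, which Section 5.1.2 allows; but the Appendix 1 slit-lamp procedure calls for no drop, so this would arise only where a site chose to use one.

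A reader might also take the row order of Table 1 as confirming the sequence. It does not: Table 1 lists the pregnancy test below BCVA, while Section 6.3 lists it above.

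**Conclusion.** The point holds as a minor one. Under the suggested order, the only acuity and slit-lamp baseline is taken after an eye drop with no stated interval. Change from baseline may then be biased if the order is followed and the tear has a transient effect. On the assumed 5% to 20% of eyes graded 1 because of the tear, a true 30% rate of new mild hyperemia would read as 28.5% to 24%. Acuity change could be shifted either way, by up to 0.10 logMAR for an assumed five-letter effect. With no tear effect the bias is nil.

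Two stronger readings are tempting. One is that vision loss or hyperemia **is** understated. The documents do not support that, because the order is not mandatory and they give no tear effect; an improvement in acuity would reverse that bias. The other is that AG-920 is favoured over placebo. That does not follow either: the tear goes into both eyes of every subject before randomization, so any effect attenuates the hyperemia difference in proportion and cancels from the difference in mean acuity change. The primary endpoint and sample size are unaffected.

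**What to change.** In Protocol Section 6.3, require (not suggest) that BCVA and slit-lamp examination come before the artificial-tear step, and that the tear step come before any tonometry anesthetic and IOP measurement, since an anesthetized eye could hide intolerance. In Appendix 1, add the artificial tear to the list of things that acuity testing must precede. Table 1 needs no change, because its rows are not a sequence.

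The cost is a reordered bullet and a few added words, with no new procedure or data. The downside is that subjects who then fail the tear test will already have had BCVA and slit lamp.

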6.4.1 Pre-dose

The following procedures will be performed in the following order at Visit 2, if Visit 1 was not performed on the same day:

- Re-verify subject eligibility based on Inclusion/Exclusion requirements.
- Review of any changes in health (medical history and AEs) or concomitant medications (including ocular medications) if Visit 2 is not combined with Visit 1

